We will pilot Screening Wizard in two community pediatric practices using a stepped wedge design (n=2 clinics, 50 adolescents).

Hypothesis 1b: Screening Wizard will increase the rate of personalized referrals, compared to TAU. We will perform multilevel modeling to explore time effects and intervention-level factors associated with Screening Wizard. We will first conduct t-tests for continuous variables and chi-square tests for categorical variables to examine for baseline differences in demographic and clinical variables. We will use generalized linear mixed models (nesting for site) to examine for between-intervention differences in personalized referral rate. Baseline characteristics distinguishing groups will be included as covariates in models examining treatment effects. Criterion for success: 75% of PCP recommendations partially or completely match Screening Wizard personalized referral and there is a 50% increase in number of parents and adolescents who feel their needs were met after the PCP visit during the Screening Wizard phase compared to TAU.

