## **Statistical Considerations**

A stepped wedge design was selected for both ethical considerations and feasibility. A stepped wedge cluster randomized trial design involves the sequential random rollout of an intervention over multiple time periods following a “baseline” period when no cluster has been exposed. The crossover is typically in one direction, from control to intervention, and continues until all of the clusters receive the intervention with observations taken from every cluster and at each time period. All 3 studies in the ETUDES Center, and specifically, Screening Wizard, will utilize this design. Prior to study start, each CCP study practice will be randomly assigned to switch from Treatment As Usual (TAU) to the intervention.

In the proposed stepped wedge design, all practices start with TAU (i.e., PCP referral to embedded MH care) and are randomized to transition to implement Screening Wizard at different times. All clinics will be initially monitored for at least 2 months during TAU, followed by a staggered adoption of Screening Wizard. During each time period, a new clinic will begin to use Screening Wizard (order determined by block randomization). A web-based system will randomly assign the next clinic to begin.

Hypothesis 1b: Screening Wizard will increase the rate of personalized referrals, compared to TAU. We will perform multilevel modeling to explore time effects and intervention-level factors associated with Screening Wizard. We will first conduct t-tests for continuous variables and chi-square tests for categorical variables to examine for baseline differences in demographic and clinical variables. We will use generalized linear mixed models (nesting for site) to examine for between-intervention differences in personalized referral rate. Baseline characteristics distinguishing groups will be included as covariates in models examining treatment effects. Criterion for success: 75% of PCP recommendations partially or completely match Screening Wizard personalized referral and there is a 50% increase in number of parents and adolescents who feel their needs were met after the PCP visit during the Screening Wizard phase compared to TAU.

Due to the pilot nature of this study, sample size and power considerations center around the precision of confidence interval (CI) width estimation for feasibility outcomes. In the Development Phase (Aim 1), a sample size of 50 affords us a 95% CI width of no more than 0.28.

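### The Hypothesis 1b mixed model nests by site with only two clinics, so site adjustment often drops out and part of any clinic difference enters the Screening Wizard estimate for the rollout order realised

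*Combined protocol and SAP*

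**What the plan says.** The design is fixed under Study Objectives: "We will pilot Screening Wizard in two community pediatric practices using a stepped wedge design (n=2 clinics, 50 adolescents". Statistical Considerations says that the practices "are randomized to transition to implement Screening Wizard at different times", and adds: "During each time period, a new clinic will begin to use Screening Wizard (order determined by block randomization". With two clinics this gives three periods: both on TAU, one on each condition, both on SW.

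The model for Hypothesis 1b appears in the same words under Study Objectives and Statistical Considerations: "We will use generalized linear mixed models (nesting for site) to examine for between-intervention differences in personalized referral rate". Just before it comes: "We will perform multilevel modeling to explore time effects and intervention-level factors associated with Screening Wizard". Site is the only grouping named. Whether period is a term in the main model is not stated.

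The covariate rule is: "Baseline characteristics distinguishing groups will be included as covariates in models examining treatment effects". It follows tests of demographic and clinical variables and does not name clinic. The plan gives no fixed clinic term, no small-cluster correction and no fallback for a zero site variance.

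**The concern.** A between-site variance estimated from two clinics rests on one degree of freedom, and its maximum-likelihood estimate is often exactly zero. The fit is then ordinary logistic regression with no site term. Whether the analysis adjusts for clinic is thus decided by noise in the data.

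This matters because clinic and phase are linked by design. With equal periods, the clinic that switches first supplies two thirds of the SW visits and one third of the TAU visits. If its match rate is higher for reasons unrelated to SW, the SW estimate is pushed up; if lower, pushed down. At stake is the point estimate that answers the pilot's only stated comparative hypothesis.

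**Working it through.** **The plan's own figure.** The stated width of 0.28 for n = 50 is the Wald width at p = 0.5: 2 × 1.96 × √(0.25/50) = 0.277. It reproduces, but it concerns a single proportion and is not an input to the Hypothesis 1b model.

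**Inputs from the documents.** Two clinics, 50 adolescents, one clinic switching per step, a mixed model nested by site, time effects to be explored.

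**Assumptions, since the documents give no figures.** Equal periods, so 25 youths per clinic in cells of 8 or 9; an average match rate of 50%; no true SW effect; the higher clinic switches first; a clinic gap over a range of values.

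**What happens when the variance is zero: algebra.** Take clinic rates of 60% and 40%, a gap of 2 × ln(0.6/0.4) = 0.81 logits.

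- *Without period.* Expected SW rate = (2/3)(0.6) + (1/3)(0.4) = 0.533. Expected TAU rate = (1/3)(0.6) + (2/3)(0.4) = 0.467. Spurious log odds ratio = 2 × ln(0.533/0.467) ≈ 0.27, about one third of the gap.
- *With period.* In periods 1 and 3 both clinics are on the same condition, so those periods say nothing about SW. The SW effect is identified only in period 2, where it is the difference between the clinics. The whole gap of 0.81 passes through.

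**How often it happens, and the net bias.** Each simulated trial was fitted by a random-intercept logistic model (maximum likelihood, Gauss-Hermite quadrature) and by a logistic model with clinic fixed. Bias is in the SW log odds ratio.

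| Run | Clinic gap (logits) | Period terms | Variance zero | Bias, random site | Bias, fixed clinic |
|---|---|---|---|---|---|
| A | 1.0 | no | 46% | +0.20 | -0.01 |
| A | 1.0 | yes | 59% | +0.63 | -0.04 |
| A | 0.5 | yes | not listed | +0.43 | +0.02 |
| B | 0.81 | no | 56% | +0.18 | +0.05 |
| B | 0.81 | yes | 63% | +0.59 | -0.01 |
| C | 1.0 | no | 46% | +0.16 | -0.04 |
| C | 1.0 | yes | 57% | +0.59 | -0.09 |

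Run A: cells 8/9/8, 1,500 to 2,500 trials per setting, mean bias, up to 4% of trials dropped as nearly separated. Run B: cells of 8, 8 and 9, 400 trials per setting, median bias, up to about 18% dropped when period is modelled. Run C repeats the 8/9/8 setting, mean bias. At a gap of 0.5 the variance is zero in up to about 74% of trials without period and 81% with it.

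**Check against the algebra (run B, zero-variance fits only).** Median bias is +0.30 without period, close to 0.27, and +1.02 with period (odds ratio exp(1.02) ≈ 2.8). The second exceeds 0.81 partly because small cells allow only a few values: 5 of 8 against 3 of 8 gives 2 × ln(5/3) = 1.02. With site effects drawn at random, the slope of the SW error on the true clinic gap in zero-variance fits is 0.95 to 1.13 with period and 0.25 to 0.41 without, as the algebra predicts. Over all fits it is 0.35 to 0.50 with period and 0.11 to 0.15 without.

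**Collapse when site effects are truly random (run B, with / without period).** ICC about 0.05: 78% / 68%. About 0.10: 70% / 61%. About 0.20: 57% / 49%.

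**Where it eases.** Collapse becomes rarer as the gap grows: 41% / 26% at 1.25 logits and 18% / 9% at 1.70.

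**The case against.** The other side has good points, and most limit the size of the problem.

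- *The order is randomised.* Averaged over both orders, mean bias is between -0.03 and +0.04. This stands as a property of the procedure. The trial, however, realises one order and reports one estimate.
- *Error rates.* A reader might infer serious false-positive inflation. The documents do not support that. They state no one-sided test and no alpha. With the higher clinic first and a 1.0 logit gap, a one-sided 2.5% test rejects in 5.2% (5.9% with period). Over both orders the rates are 2.0% to 3.9% for gaps of 0.5 and 1.0. Two-sided rates are 4.3% to 5.1% in three of four settings and 7.3% in the worst. Non-coverage of the 95% interval in run B is about 2% to 8%.
- *Full carry-over.* A reader might infer that the clinic difference passes whole into the SW effect. That is essentially so only when the variance is zero and period is modelled, and the plan says only that time effects will be explored.
- *Accuracy.* Over both orders, RMSE for random against fixed site is 0.62 v 0.66 (gap 0.5) and 0.67 v 0.68 (gap 1.0) without period, and 1.25 v 1.38 and 1.44 v 1.34 with period. Fixed clinic trades variance for freedom from order-dependent bias; it does not win on RMSE throughout.
- *The pilot's conclusion.* Success is judged on "75% of PCP recommendations partially or completely match Screening Wizard personalized referral" and on a 50% rise in families reporting that their needs were met. Neither is this model's coefficient.
- *Wording.* The phrase random effect does not appear. It remains the ordinary reading of a mixed model nested by site. Nor do the documents claim inference to clinics in general, so that should not be held against them.

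What is left is a model whose adjustment for clinic depends on chance, for the one comparison the plan sets out to estimate.

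**Conclusion.** The concern holds in limited form and merits a should-fix. For clinic gaps of 0.5 to 1.0 logits, site adjustment disappears in roughly half to four fifths of trials. In the order realised, the SW log odds ratio then shifts on average by about 0.1 to 0.2 without period and 0.4 to 0.6 with it, upward or downward according to which clinic switches first. Against standard errors of about 0.6 and 1.1, that is a visible distortion of the estimate but not a breakdown of the test. The sizes rest on assumed clinic rates, equal periods and the random-intercept reading. The mechanism does not depend on the particular rates: it needs only two clinics that differ, a staggered switch and a zero variance estimate.

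**What to change.** Under both Study Objectives and Statistical Considerations, replace the site-nested mixed model for Hypothesis 1b with wording such as: *The match outcome will be analysed by logistic regression (or a cumulative-logit model for the three match categories) with SW phase and a fixed indicator for clinic, using Firth-type penalisation if cells are sparse. Clinic will remain a fixed term in any model that includes period. The SW effect will be reported as an estimate with its 95% confidence interval and applies to these two clinics.* State in advance whether period is in the main model, because the problem is largest there.

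No extra participants and no design change are needed. The cost is precision. The median SE rises from about 0.58 to 0.63 without period and from about 1.10 to 1.30 with period. On the odds-ratio scale, the 95% limits move from a factor of exp(1.96 × 0.58) ≈ 3.1 to exp(1.96 × 0.63) ≈ 3.4 either side of the estimate, and from about 8.6 to about 12.8 with period. When the clinic gap is small, RMSE is also slightly larger. A fixed clinic term removes the carry-over; it does not extend the result beyond the two clinics.

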
Screening Wizard will be developed with iterative feedback from end-users (both families and PCPs) using principles of user-centered design with the assistance of the ETUDES Methods Core in conducting qualitative studies described below. A decision tree based on available evidence and expert consensus will determine personalized treatment recommendations with input from the measures as described above. The flowchart for the decision tree will be refined during the usability (phase 1a) and feasibility (phase 1b) phases of the study and will include an immediate referral to a suicidality intervention provided by the primary care clinic staff if high suicidality is identified by PHQ-9 item 9 and the adaptive suicide assessment. The decision tree will prioritize decisions as to how quickly patients should be seen, and in what sector based on suicidality, depression severity, parent perception of adolescent functioning, and presence of

comorbidities. The default treatment recommendations made based on depression severity will then be modified based on: 1) readiness for treatment and 2) treatment preference considering A) congruence between the adolescent and parent, B) depression knowledge, and C) identified barriers. We will also inquire about family history of bipolar illness. The NuReIm team and Methods Core will support integration with the Epic EHR at this stage.

In the Phase 1b, Feasibility, we will test the feasibility of using Screening Wizard in two community pediatric practices (n=50) using a stepped wedge design. We hypothesize that participants, parents, and clinicians will find the intervention usable and feasible to deploy.

To operationalize the main outcome, we will review the EHR for the treatment recommendation made by the PCP and categorize it as: 1) PCP recommendations matches Screening Wizard referral; 2) PCP recommendation partially matches Screening Wizard referral; or 3) PCP recommendation does not match Screening Wizard referral.

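### The match outcome is a PCP decision, but the plan clusters only by site and its 0.28 precision figure assumes 50 independent youths (minor)

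*Combined protocol and SAP*

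**What the plan says.** - **Outcome.** Study Design & Methods makes the PCP the source of the main outcome: "we will review the EHR for the treatment recommendation made by the PCP". The recommendation is then coded as match, partial match or no match with the Screening Wizard referral.
- **Model.** Statistical Considerations states: "We will use generalized linear mixed models (nesting for site) to examine for between-intervention differences in personalized referral rate". The same sentence stands under Hypothesis 1b in Study Objectives. A multilevel model is also mentioned, but for time trends and factors at the intervention level. No PCP term, PCP-clustered variance, PCP count or ICC is given.
- **Precision.** Also in Statistical Considerations, "sample size and power considerations center around the precision of confidence interval (CI) width estimation for feasibility outcomes", followed by the figure itself: "a sample size of 50 affords us a 95% CI width of no more than 0.28". That sentence labels the phase as development, Aim 1. It does not name the match rate and does not say that the figure comes from the mixed model.
- **Setting.** There are two clinics and 50 adolescents. Every clinic starts in treatment as usual (TAU) and later switches to Screening Wizard.
- **Success criterion.** One part is that 75% of PCP recommendations agree fully or partly with the tool.

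**The concern.** Screening Wizard works by giving the PCP information and decision support, and the outcome is what the PCP then does. PCPs are likely to differ in referral habits and in how far they follow a tool, so two youths seen by one PCP may well have more similar outcomes than two youths seen by different PCPs at the same clinic. A model that names only site treats them as independent once site is known.

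The consequence is clearest for a single proportion. If a few PCPs see most of the 50 youths, the match rate carries the information of fewer than 50 independent decisions. An interval that ignores this makes the result look firmer than it is, and the match rate is one of the figures on which the pilot will be judged.

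**Working it through.** **Inputs from the documents:** n = 50 youths, 2 clinics, 95% interval, stated maximum width 0.28, match criterion 75%.

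**Assumptions, because the documents are silent:** p = 0.5 for the stated width (the worst case, which an upper bound implies); 5 to 20 PCPs in total; PCP-level ICC 0.05 to 0.20; equal numbers of youths per PCP.

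**1. Reproduce the plan's figure.** Wald width = 2 × 1.96 × sqrt(p(1 − p)/n) = 2 × 1.96 × sqrt(0.25/50) = 0.277, which rounds to 0.28. The design effect is 1, so the figure allows for neither PCP nor site clustering.

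**2. Margin.** The width passes 0.28 once the design effect exceeds (0.28/0.2772)² = 1.02. With 5 youths per PCP, 1 + 4 × ICC = 1.02 gives an ICC of 0.005.

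**3. Maximum width with PCP clustering.** Design effect = 1 + (m − 1) × ICC, where m = 50/number of PCPs; width = 0.277 × sqrt(design effect). For example, with 10 PCPs and ICC 0.10 the design effect is 1.40 and the width is 0.277 × sqrt(1.40) = 0.328.

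| PCPs | Youths per PCP | ICC 0.05 | ICC 0.10 | ICC 0.20 |
|---|---|---|---|---|
| 20 | 2.5 | 0.287 | 0.297 | 0.316 |
| 10 | 5 | 0.304 | 0.328 | 0.372 |
| 5 | 10 | 0.334 | 0.382 | 0.464 |

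**4. Width at the 75% criterion.** With all 50 youths, the unclustered width at p = 0.75 is 0.240. With 10 PCPs it is 0.263, 0.284 and 0.322 at the three ICCs, so at that proportion the 0.28 bound fails only from an ICC of roughly 0.09 upward ((0.28/0.240)² = 1.36 = 1 + 4 × 0.09). If only the Screening Wizard visits count and they are half the sample (assumed 25), the width is 0.339 before any clustering, 0.352 to 0.387 with 10 PCPs and 0.372 to 0.455 with 5.

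**5. Coverage.** In simulation of a true match rate of 75%, with 6 to 20 PCPs and ICC 0.05 to 0.20, unclustered nominal 95% intervals covered about 77% to 94%.

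**6. TAU versus Screening Wizard.** A linear approximation (2 clinics, 3 periods, 50 youths, 3 to 8 PCPs per clinic) compared the standard error from a site-adjusted model with the true one:

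| PCP pattern | Site-adjusted SE / true SE |
|---|---|
| Same PCPs in both phases, constant PCP effect | 0.99 to 1.00 |
| Same PCPs, but they respond differently to the tool | 0.85 to 0.99 |
| Each PCP seen in one condition only | 0.59 to 0.97 |

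**7. Would a PCP random intercept help the contrast?** With PCP-specific response (SD 0.8 and 1.2 on the logit scale; 3, 5 or 10 PCPs per clinic; 400 runs per setting, Monte Carlo error about 0.01), coverage was 0.90–0.95 for the site-adjusted model, 0.89–0.93 with a PCP random intercept and 0.91–0.95 with PCP-cluster-robust standard errors.

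**The case against.** A reader might infer that the site-only model makes all the trial's intervals too narrow, the 0.28 among them. The documents do not support that, for two reasons.

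- **The 0.28 is a separate calculation.** It is a one-proportion width for feasibility outcomes in general and ignores site as well as PCP. Adding a PCP term to the mixed model would leave it unchanged.
- **The quoted model is for the phase comparison.** Because every clinic crosses over, a constant PCP effect largely cancels when the same PCPs work in both phases. Under-coverage then needs PCPs who respond differently to the tool. The documents neither say this nor rule it out, and they do not say that the same PCPs see youths in both phases.

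Three further objections stand. The size of the error depends on PCP numbers and an ICC that the plan does not give; with 20 PCPs and ICC 0.05 the width is 0.287, which is trivial against 0.28. The 75% criterion is a point threshold, so clustering changes its stated uncertainty and not whether the observed proportion reaches 75%. And this is a two-clinic pilot sized for precision, not a confirmatory test.

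What the objections do not answer is that the match rate is a proportion of PCP decisions, and nothing in the plan allows for correlation within a PCP when its precision is stated or reported.

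**Conclusion.** The point holds in a limited form and is minor. The stated 0.28 is correct for 50 independent observations and has almost no room for correlation. If outcomes are correlated within PCP, it is too small as a worst-case width for the match proportion: 0.29–0.32 with 20 PCPs, 0.30–0.37 with 10 and 0.33–0.46 with 5, over an assumed ICC of 0.05 to 0.20. An unclustered interval for that proportion then under-covers.

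For the phase comparison the error is conditional. It is near zero with stable PCPs and a constant PCP effect, and it matters if response to the tool varies by PCP or PCPs appear mainly in one phase. The documents do not show which applies. The smaller number of Screening Wizard visits may cost more precision than PCP clustering does; that adds to the problem and does not replace it.

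**What to change.** 1. **Match proportion.** Report it with a PCP-clustered interval that has a small-sample correction. Take PCP identity from the EHR review; it should be available there, but the documents do not say so and this needs confirming.
2. **Precision sentence.** State that 0.28 holds only for 50 independent observations, and show the width over a range of PCP counts and ICCs, as in the first table above.
3. **Phase comparison.** Add a sensitivity analysis with small-sample PCP-cluster-robust standard errors. Do not rely on a PCP random intercept, which does not address differing response and did no better in simulation. Robust errors gave no consistent gain either, which is why this belongs in a sensitivity analysis.

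Whether to add fixed period effects is a separate question and not part of this change. In an assumed layout of 2 clinics and 3 periods they roughly double the standard error of the phase effect (0.30 to 0.60 residual SDs).

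The cost is SAP wording, one identifier per visit, somewhat wider intervals and a less favourable stated precision.

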## Scientific Background

Depression is the single most important contributor to suicidal ideation, attempt, and death by suicide among adolescents. Consequently, the United States Preventive Services Task Force (USPSTF) recommends that all adolescents be screened annually for major depression when formal procedures are in place to follow-up on a positive test. These recommendations have been implemented at Children's Community Pediatric (CCP) practices where adolescents who present for routine care are requested to complete the PHQ-9 depression screen on a tablet computer handed to them as a part of routine care, and embedded mental health services are present. Embedded mental health services refers to mental health services that occur within the pediatric primary care office (referring to a therapist or other mental health provider being housed within the same facility as medical providers). All practices within CCP from which this project will recruit have embedded mental health providers available, on-site. However, remaining challenges are that pediatric primary care providers (PCPs) are uncertain about how to: (1) interpret the results of screens and, (2) assess and integrate information about patient beliefs, preferences and barriers to guide their management decisions as recommended by the latest Guidelines for Adolescent Depression in Primary Care (GLAD-PC). These challenges may account for making referrals that are a less-than-ideal fit for the patient and may partially account for low rates of treatment adherence in patients who screen positive for depression. Screening Wizard aims to design and test an automated decision-support system that will provide PCPs with this information and facilitate "formal procedures to follow-up on a positive test" as recommended by the USPSTF.

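### Hypothesis 1b covariates enter the model only if a baseline test flags them, with no cutoff and none always included; adding PHQ-9 as a fixed covariate and keeping the screen is a cheap, minor improvement

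*Combined protocol and SAP*

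**What the plan says.** The Hypothesis 1b text appears under Study Objectives and again under Statistical Considerations. The first step is: "We will first conduct t-tests for continuous variables and chi-square tests for categorical variables to examine for baseline differences in demographic and clinical variables". A generalized linear mixed model with nesting for site then compares the phases, and "Baseline characteristics distinguishing groups will be included as covariates in models examining treatment effects". There is no significance level, no other definition of what counts as distinguishing, and no list of covariates.

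The pilot has two clinics and 50 adolescents. Statistical Considerations randomises the order in which clinics switch. The split of youths between phases is not given.

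For the main outcome, Study Design & Methods says "we will review the EHR for the treatment recommendation made by the PCP and categorize it as" a match, a partial match or no match with the Screening Wizard referral. On how that referral is built, it says: "The default treatment recommendations made based on depression severity will then be modified". Scientific Background says that adolescents at these practices "are requested to complete the PHQ-9 depression screen on a tablet computer handed to them as a part of routine care", and Study Design & Methods has PCPs receiving the PHQ-9 score during TAU.

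On size, the plan says that "sample size and power considerations center around the precision of confidence interval (CI) width estimation for feasibility outcomes". One success criterion reads: "Criterion for success: 75% of PCP recommendations partially or completely match Screening Wizard personalized referral". The other is a 50% increase in parents and adolescents who feel their needs were met.

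**The concern.** Omitting a covariate biases the contrast when two things hold together: the phases differ on it, and it predicts the outcome. The plan's rule looks only at the first, through a significance test with few subjects. A variable that predicts match, with a modest imbalance, can therefore be left out.

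Imbalance is a live possibility. Only the switch order of two clinics is randomised, so TAU youths and Screening Wizard youths are not randomised against each other.

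There is also a specification gap. Without a cutoff or a fixed covariate, two analysts could fit different Hypothesis 1b models to the same data. What is at stake is the adjusted estimate of the difference in match rate.

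**Working it through.** **1. The plan's own figure.** The only sample-size figure is a 95% CI width of at most 0.28 with n = 50. The Wald full width at p = 0.5 is 2 × 1.96 × √(0.25/50) = 0.277, so it reproduces. The plan gives no power for the baseline tests.

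**2. How often the screen flags a true imbalance.** Inputs: 50 youths (plan); two-sided cutoff and phase split (assumed). For a t-test with true difference d in SD units, the noncentrality is d × √(n1 × n2/(n1 + n2)) with n1 + n2 − 2 = 48 df. At 25/25 and d = 0.5 it is 0.5 × √12.5 = 1.77. At 10/40 it is 0.5 × √8 = 1.41.

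| Quantity | Cutoff 0.05 | 0.10 | 0.20 |
|---|---|---|---|
| 0.3 SD flagged, 25/25 | 18% | 28% | 42% |
| 0.5 SD flagged, 25/25 | 41% | 54% | 68% |
| 0.5 SD flagged, 10/40 | 28% | 40% | 55% |
| True difference flagged half the time, 25/25 | 0.57 SD | 0.47 SD | 0.36 SD |
| Same, 10/40 | 0.71 SD | 0.59 SD | 0.45 SD |
| 30% v 50%, uncorrected chi-square, 25/25 | 33% | 45% | 57% |

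Of the splits checked, 25/25 is the most favourable to the screen.

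**3. Bias left in the contrast.** Assumed: match as a yes/no outcome, a 0.5 SD phase imbalance in one predictive covariate, one balanced covariate that does not predict, 25/25, no true effect, two clinics by three periods. The model was logistic with treatment, a fixed clinic term and whichever covariates the rule admits. The effect was a marginal risk difference, with 10,000 runs per setting.

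| Bias, percentage points | OR 1.5 per SD | OR 2 | OR 3 |
|---|---|---|---|
| Rule at 0.05 | 1.7 | 3.0 | 3.9 |
| Rule at 0.10 | 1.1 | 2.0 | 2.4 |
| Rule at 0.20 | 0.5 | 1.1 | 1.1 |

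With the predictive covariate always included, bias lies between −0.1 and 0.2. RMSE, rule at 0.05 v always included, is 15.6 v 15.6, 15.3 v 14.8 and 15.3 v 14.2. A separate run with another assumed layout gave bias of 1.7, 2.8 and 4.1 under the rule.

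Variations: with true match of 50% under TAU and 75% under Screening Wizard, the rule leaves 1.5, 2.6 and 4.0 points. At 10/40 with no effect it leaves 3.0, 3.9 and 5.3, with RMSE near 18. With no expected imbalance there is no bias either way.

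For scale, a bias of 3 on an SD of 15 gives an RMSE of √(15² + 3²) = 15.3.

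**4. What should replace the rule.** Suppose a short fixed list replaces the screen and the imbalanced predictor is not on it. Two separate sets of runs, with the rule at 0.05, gave this bias in points:

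| | OR 1.5 | OR 2 | OR 3 |
|---|---|---|---|
| List alone, first set | 4.9 | 7.8 | 10.7 |
| Present rule, first set | 1.7 | 3.0 | 3.7 |
| List alone, second set | 5.1 | 7.6 | 11.6 |
| Present rule, second set | 2.2 | 3.0 | 5.0 |

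In the first set, RMSE was 16.2 v 15.5, 17.1 v 15.3 and 18.8 v 15.1 (list v rule). The losses of 0.7, 1.8 and 3.7 exceed the gains of 0.0, 0.5 and 1.1 that step 3 shows for a correct list.

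Always including PHQ-9 and keeping the screen avoids this. Bias is near 0 if PHQ-9 is the predictor and level with the present rule if it is not. In the latter case the RMSE cost is about 0.1 to 0.2 on 15.

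**5. Does modelling time remove the problem?** The plan also says: "We will perform multilevel modeling to explore time effects and intervention-level factors associated with Screening Wizard". In a linear-probability sensitivity run (0.5 SD, 25/25, rule at 0.05, OR 1.5, 2, 3), period terms changed the bias from drift shared by both clinics from 2.4, 3.9, 5.4 to −1.2, −1.9, −2.3. For imbalance tied to phase itself, 1.8, 2.9 and 4.2 points remained with period terms in the model. Period terms also raised the SD from about 15 to about 27 to 30 points. Whether the effect model should carry them is a separate question.

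**The case against.** The strongest objection is to the remedy that first suggests itself. A reader might infer that the screen should be dropped for a short pre-named list. The documents do not support that. They show nowhere that PHQ-9 or any other named variable drives match, and the plan screens a wider set of demographic and clinical variables. Step 4 shows the loss when the list is wrong. This objection stands and shapes the fix.

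A reader might also take PHQ-9 to be an established predictor of match. Study Design & Methods says that depression severity sets the default recommendation, not that it predicts whether the PCP agrees. PHQ-9 is plausible and available in both phases, but the strength of the link is unknown.

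It can fairly be said that the benefit is small even with the right covariate. At OR 1.5 the RMSEs are equal, and with a 50% to 75% effect the rule is slightly ahead (14.7 v 14.9). A clear gain needs an assumed 0.5 SD imbalance and an OR of 2 to 3. The 0.57 SD figure also refers to a true imbalance, whereas what distorts a given estimate is the observed one, and the test does flag observed differences above about that size. Both remarks stand and limit the point to a minor one.

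That this is only a pilot is a weaker defence. The plan commits to an adjusted phase comparison, so its model should be fixed before the data are seen.

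**Conclusion.** The point holds as a minor one. The missing cutoff and the absence of any always-included covariate are plain in the text, and the detection rates follow from n = 50 once a split and a cutoff are assumed. The residual bias of about 2 to 4 percentage points (3 to 5 at 10/40) rests on assumptions not in the documents: a 0.05 cutoff, a 0.5 SD imbalance, an OR of 1.5 to 3 per SD and the clinic-by-period layout. It is small against an SD near 15 at 25/25, and smaller still at a looser cutoff.

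A reader might go further and conclude that the sample size, the go/no-go decision or the main analysis is unsound. The documents do not support that. The 75% match and 50% needs-met criteria carry no adjustment and are unaffected, and the sample size rests on CI width, not on this contrast.

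**What to change.** In the Hypothesis 1b text under both Study Objectives and Statistical Considerations:

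- Include continuous PHQ-9 total in the model whatever its observed balance, and keep the site term.
- Keep the baseline comparison as a supplementary way to add other imbalanced variables. List the variables to be screened and fix the threshold in advance, for example as a standardised difference.
- Do not replace the screen with a short list alone.

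For orientation on the threshold: at 25/25 the smallest observed difference that reaches significance is about 0.57 SD at 0.05 and 0.37 SD at 0.20. A looser threshold leaves less bias but admits more variables by chance. With five independent balanced variables, the probability that at least one is flagged is 1 − 0.95⁵ = 23% at 0.05 and 1 − 0.80⁵ = 67% at 0.20. The screened set should therefore stay short.

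The cost is wording in two places and no new data, since PHQ-9 is collected in routine care. The downside is one extra covariate in a 50-person binary model, worth about 0.1 to 0.2 RMSE points on 15 if PHQ-9 does not predict match.
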